**SECTION 2. Assessment and Evaluation of the Risks**

For details, refer to the UK IRB's [Policy on Children in Research](#).

A. Provide justification for the participation of children as research subjects in your study.

We are investigating the effect to their infants of moringa oleifera leaf supplementation to breastfeeding mothers. Infants are thus required participants

B. Has this research been conducted in adults?  Yes  No

If yes, is there any indication that the proposed research would benefit, or at least not be harmful to children?

Multiple generations of traditional use of moringa oleifera by adults, children, animals; many studies utilizing moringa oleifera leaf with no significant safety concern to breastfeeding mother or children

C. Indicate how many children you propose to enroll in the study: 320

**Note:** Whenever possible, involve the fewest number of children necessary to obtain statistically significant data which will contribute to a meaningful analysis relative to the purpose of the study.

Justify this number:

In the United States as an example of a mostly well-resourced population, stunting prevalence in children under five years is 3.5% (UNICEF data from last census 2016).(44) In comparison, in a 2019 cross-sectional survey of Pamoja CBO recipient population in Kisumu (unpublished data, Pamoja CBO 2019) stunting prevalence is 25% in children <5 years. This is comparable to the most recent national level Kenyan data of the region that contains Kisumu (Nyanza region) from the 2014 Kenyan National Demographic Health Survey showing a stunting prevalence of 24.9% in children <5 years of age.(45) We hypothesize that we will see a 75% reduction in stunting prevalence (<-2 LAZ) at 3 months of age in children with moringa-supplemented breastmilk versus controls. We think that moringa supplementation will

increase breastmilk volumes thus increasing infant growth and may lead to improved intestinal health leading to increased absorption of nutrients consumed. Thus, we estimate a change from estimated 25% stunting prevalence to 6.5% stunting; in comparison, this is still double the prevalence of stunting in children under five years in the United States (3.5% UNICEF data 2016). At 80% power, this would require a sample size of 82 infants in each arm. Due to concern for loss to follow up and a possibility of a smaller effect than estimated, we aim to recruit 100 infants in each arm if external funding is obtained. That is 200 infants. We also estimate 50 children 6-59 months in each arm, that is 100 children. We also estimate 10-20 children trying moringa and placebo for the acceptability study. That is a total of 320 children.

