## Background

Include a brief review of existing literature in the area of your research. You should identify gaps in knowledge that should be addressed and explain how your research will address those gaps or contribute to existing knowledge in this area. For interventional research, search PubMed and ClinicalTrials.gov for duplicative ongoing and completed trials with same condition and intervention(s).

**Background and Significance.** Childhood undernutrition (low weight for age, low height for age, low weight for height, or micronutrient deficiencies) contributes up to 45% of deaths globally in children under five years and negatively impacts individual and societal health by impairment of long-term health, cognitive capacity, productivity and wage-earning force. Identification of effective, locally available, low-cost, and readily scalable interventions for its prevention remains elusive. Undernutrition may begin in utero due to maternal undernutrition and micronutrient deficiencies. After birth, poor nutrient intake, frequent infectious disease, and poor intestinal health lead to ongoing impaired growth and psychomotor-cognitive development. Intestinal inflammation and reduced gut integrity from chronic exposure to intestinal pathogens leads to Environmental Enteric Dysfunction or EED (aka "tropical sprue"). Large-scale research has increasingly established the role of intestinal inflammation and a leaky gut in stunting, reduced efficacy of oral vaccines, reduced absorption of nutrients, intestinal dysbiosis, and increased morbidity and mortality in childhood undernutrition.

Early intervention within the first 1000 days of life from conception to 24 months may mitigate or reverse the adverse impact of undernutrition and its associated complications. Interventions after 24 months are additionally important to prevent or reverse worsening undernutrition. Potential targets include improving breastmilk quality and quantity for exclusively-breastfeeding infants, increasing the nutrient density of complementary foods for infants and children over 6 months of age, and optimizing intestinal and systemic inflammation to improve nutrient absorption and reduce nutritional needs in all age groups. Accessible and practical interventions that address multiple determinants of undernutrition in regions with high prevalence of maternal and child undernutrition such as the western Kenyan state of Kisumu are a priority.

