**Relevance to Kisumu, Kenya:** Our target subjects of Kisumu, Kenya are a rural population with poor water, sanitation, hygiene, high rates of undernutrition and limited access to health resources. They have low Dietary Diversity (availability of adequate varied food groups) leading to additional micronutrient deficiencies. They are mostly subsistence farmers who are not universally acquainted with *moringa* cultivation or consumption, however we have recently completed a study in Kisumu that shows excellent acceptance and uptake of *moringa* intensive leaf cultivation and a positive attitude to dried leaf powder consumption ([name] and [name], manuscript in progress 2020). The wider Kisumu population is the target area of our partner Pamoja Community Based Organization (Pamoja, executive director [name]), which spans three districts in the region of Kisumu comprising some of the highest-needs populations in Kenya. In a 2019 baseline survey of 469 0-59 month old children within Pamoja's catchment area, 25% were stunted, 8% wasted, and 13% underweight (unpublished data, personal communication from [name]). Micronutrient deficiencies are not specifically defined in this population, however an estimated 69% of children under five years in Kenya are iron deficient and 20-39% are estimated to have vitamin A deficiency. Targeting undernutrition in a cost-effective manner is crucially needed in this region; our study will work with the infrastructure and trust of Pamoja and the communities it serves by testing acceptability of *moringa* leaf consumption in staple food of grain porridge, acceptability of placebo, and conducting a pilot of *moringa* leaf consumption and its effect on childhood growth, nutrition, and intestinal and systemic inflammation.

**Safety:** No trial of *moringa* leaf consumption in children or lactating women has shown significant adverse effects. Cultures all over the world and across centuries have used *moringa* leaf as food and medicine without reported ill effect at traditional doses. Seed, root, or leaf extract are not the intervention used in this study. They concentrate the biochemically active plant isothiocyanates and phytosterols

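### The only power claim for infant growth applies a 0–59-month stunting prevalence to infants at 3 months and counts stunting present at enrolment, so the 75% reduction and its 80% power are unsupported

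*Combined protocol and SAP*

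**What the plan says.** The justification for the number of children (Subject Children, Section 2.C) sets the infant growth target: "We hypothesize that we will see a 75% reduction in stunting prevalence (<-2 LAZ) at 3 months of age". It then gives the two rates, "we estimate a change from estimated 25% stunting prevalence to 6.5% stunting", and the resulting size: "At 80% power, this would require a sample size of 82 infants in each arm". It adds a recruitment aim of 100 infants per arm if external funding is obtained, to allow for loss to follow-up and a smaller effect.

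The same section gives the source of the control rate. In the partner organisation's survey, "stunting prevalence is 25% in children <5 years", and the regional survey is cited as "showing a stunting prevalence of 24.9% in children <5 years of age". The Background (Relevance to Kisumu) gives the age range of the local survey: "In a 2019 baseline survey of 469 0-59 month old children within Pamoja's catchment area, 25% were stunted". The 6.5% is set beside a United States figure of 3.5%, also for children under five.

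Infants enter within 30 days of delivery. The infant exclusions are significant congenital disease and inability to feed orally (Study Population, Phase B; Study Design). Low length at entry is not among them. The Background says: "Undernutrition may begin in utero due to maternal undernutrition and micronutrient deficiencies". Phase B of the Study Population anticipates up to 50 dyads per arm; the Study Design gives 100 pairs per arm.

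**The concern.** Two features of the endpoint pull against the target.

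First, the control rate is not matched for age. A prevalence across the first five years is used as the expected rate at 3 months, and no passage gives a rate near that age. The comparison figure for the treated rate has the same age range, so neither end of the assumed effect is tied to 3-month-olds.

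Second, the endpoint is prevalence at one early time point, not new stunting. An infant already below the cut-off at enrolment who is still below it at month 3 is an event, whatever happened to growth in between. The Background allows for a prenatal contribution, so some of the month-3 prevalence may predate the mother's first dose.

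This is the only quantitative growth target in the documents and the only power statement for infants. If it is wrong, the assurance of 80% power is wrong too, and a null result on month-3 stunting taken alone could reflect size at birth as much as growth during supplementation. For the size of the effect, the documents offer a mechanism (breastmilk volume, intestinal health) but no evidence that stunting would fall by three quarters.

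**Working it through.** **Inputs.** Control 25%, treated 6.5%, power 80%, 82 per arm, recruitment aim 100 per arm (Section 2.C); 50 dyads per arm (Study Population, Phase B); alpha 0.05 (SAP). Sidedness is not stated; two-sided is assumed. Stunting at enrolment and at 3 months is not given, so values for these are assumptions shown as ranges.

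**Formulas** (two proportions, pooled null variance, p̄ = (p1+p2)/2):

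- n per arm = [1.960·√(2p̄(1−p̄)) + 0.842·√(p1(1−p1)+p2(1−p2))]² / (p1−p2)²
- power = Φ{[|p1−p2|·√n − 1.960·√(2p̄(1−p̄))] / √(p1(1−p1)+p2(1−p2))}

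**1. The plan's own figure.** With p1 = 0.25 and p2 = 0.065, p̄ = 0.1575 and n = (1.010 + 0.419)² / 0.185² = 59.7, so 60 per arm. A continuity correction gives 71 and Fisher's exact test about 66. The stated 82 does not reproduce at 80% power; it exceeds what the plan's inputs need. At 82 per arm, power for 25% versus 6.5% is about 91%, so the sizing has some slack. The point below does not depend on this discrepancy. (6.5% is a 74% cut, since 1 − 0.065/0.25 = 0.74; an exact 75% cut would give 6.25%.)

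**2. Lower control rate, same proportional cut (p2 = 0.26·p1).** Control rates below 25% are assumptions.

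| Control | Treated | n per arm for 80% | Power, 50/arm | Power, 82/arm | Power, 100/arm |
|---|---|---|---|---|---|
| 25% (plan) | 6.5% | 60 | 73% | 91% | 95% |
| 20% | 5.2% | 78 | 61% | 82% | 89% |
| 15% | 3.9% | 108 | 47% | 68% | 77% |
| 10% | 2.6% | 169 | 33% | 50% | 58% |

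**3. Control rate really 25%, but part of it already fixed at entry.** Let f be the share of control-arm stunting that is present at enrolment and persists, and let the remainder fall by 74%. Then p2 = 0.25·[f + (1−f)·0.26].

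| f (assumed) | Treated rate | Power, 82/arm |
|---|---|---|
| 25% | 11% | 64% |
| 50% | 16% | 31% |
| 75% | 20% | 10% |

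These are scenarios, not limits. If every non-fixed case were prevented, the treated rate would be 0.25·f = 6.25%, 12.5% or 18.75%, with power at 82 per arm of 92%, 54% or 16%.

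**4. When the target passes out of reach by prevention alone.** If a proportion b of all infants is stunted at entry and stays so, the cut in new stunting needed to reach 6.5% is 1 − (0.065 − b)/(0.25 − b):

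- b = 0: 74%
- b = 5%: 92.5%
- b = 6.5%: 100%
- b = 10%: not attainable; even with no new cases, 1 − 0.065/0.10 = 35% of the persistent cases would have to be reversed

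**5. Scale of the effect.** Assuming normal length-for-age Z with equal SD, moving the share below a fixed cut-off from 25% to 6.5% needs a mean shift of 1.514 − 0.674 = 0.84 SD.

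**The case against.** The other side has several good arguments.

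- **Impossibility is not shown.** A reader might infer that no three-month postnatal trial could deliver the target. The documents do not support that. It depends on stunting at enrolment and at 3 months, and neither is reported. With almost no stunting at entry and a true 25% rate at 3 months, the target is extreme but attainable.
- **Early stunting may reverse.** A reader might also take treated rates of 11%, 16% or 20% as the lowest possible. They are not, as step 3 shows. The Background says early intervention may mitigate or reverse the effects of undernutrition, and an infant who recovers by month 3 is not an event.
- **The target is not the formal hypothesis.** The Objectives speak broadly of better infant growth and nutrition. The 75% figure appears only in the sample-size justification, and no visible text names month-3 stunting as primary. The outcome table is an attachment that is not shown.
- **Better analyses are within reach.** Lengths are measured monthly, Z scores are assigned, and the SAP analyses outcomes as change from baseline. A null stunting result would not be the only evidence on growth.
- **There is slack.** At a 20% control rate, 82 per arm still gives 82% power, and the aim of 100 per arm was set partly for a smaller effect. A control rate above 25% would raise power.

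All of this stands and limits the claim. It does not supply a control rate for the right age, a baseline stunting share, or any support for a 75% effect. The SAP also does not say how infants stunted at baseline are handled in a stunting analysis.

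**Conclusion.** The point holds in limited form. The 25% describes children aged 0–59 months, nothing in the documents ties it to 3 months, and the prevalence endpoint mixes stunting carried in from birth with growth on study. The 75% reduction is unsupported, and it is implausible unless few infants are stunted at enrolment; the threshold for prevention alone is about 6.5% persistently stunted.

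The loss of power depends on unknowns. It is negligible against the stated 80% if the control rate is 20% and 82 infants per arm are analysed. It is serious if the rate is 10% (50% power at 82 per arm, 58% at 100, 33% at 50) or if half of the control-arm stunting is fixed at entry (31% at 82 per arm when the rest falls by 74%). These figures assume a two-sided 0.05 test and the normal approximation; the control rates and fixed shares are illustrative. They show that the 80% is conditional on an unverified rate. They do not show that the trial must fail or that its growth data would be uninformative.

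**What to change.** 1. Name length-for-age Z at month 3, adjusted for length-for-age Z at enrolment, as the infant growth outcome. This uses lengths already planned, fits the SAP's change-from-baseline approach, and is more sensitive than a dichotomised prevalence.
2. Report month-3 stunting as descriptive, split by stunting at enrolment, so that new and persistent cases are seen separately.
3. In Section 2.C, state that 25% is the 0–59-month prevalence and not an expected rate at 3 months. Withdraw the 75% reduction and its 80% power, or restate both as conditional on that rate. Reconcile the 82 per arm with the stated power in the same edit.

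**Cost.** Changes to the protocol and SAP text, with no new measurement. The headline becomes less striking than stunting prevented. Because the SAP is written in the past tense, any outcome named after data were seen must be disclosed as post hoc.

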**Short Title Description**

Please use a few key words to easily identify your study - this text will be displayed in the Dashboard listing for your study.

Moringa Kenya Pilot

Anticipated Ending Date of Research Project: 12/30/2022

Maximum number of human subjects (or records/specimens to be reviewed) 104

After approval, will the study be open to enrollment of new subjects or new data/specimen collection?  Yes  No

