**Phase B) Pilot RCT**

Inclusion criteria: lactating women of at least 18 years of age and their exclusively breastfed infants within 30 days of delivery with informed consent. Children 6-59 months who are orally feeding with caregiver informed consent.

Exclusion criteria: regular maternal consumption of moringa in the month prior to study enrollment, receipt and consumption of food supplementation program, or inability to feed orally; for infant, significant congenital disease, inability to feed orally. For child: inability to feed orally or refusal to eat porridge (>3 days consecutively).

We anticipate enrolling up to 50 mother-infant dyads in each of two arms and 50 children in each of two arms.

We propose starting enrollment as soon as all ethical approvals obtained, personnel hired, and study supplies obtained; there is no additional sample composition of subjects. This study targets women and infants as breastfeeding infants have the potential to receive the greatest benefit from moringa leaf supplementation to their lactating mothers.

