### We will implement:

A) a short acceptability study of acceptability, adherence, and preference for moringa dried leaf consumption and placebo consumption in porridge. Selection will be from lactating women 18 years and over and children 6-59 months; subjects will come from our target region of Kisumu.

B) a pilot placebo-controlled RCT of mother-infant dyads and their children 6-59 months who present for first postnatal check to two high volume rural maternal and child health centers in Kisumu, Kenya.

Inclusion criteria: lactating women of at least 18 years of age and their exclusively breastfed infants within 30 days of delivery with informed consent. Children 6-59 months of age who are eating food.

Exclusion criteria: regular maternal consumption of moringa, receipt and consumption of food supplementation program, or inability to feed orally; for infant, significant congenital disease, inability to feed orally. For mother or child: inability to orally feed or complete refusal (>3 days) to eat moringa or placebo porridge.

Sample size: 100 infant-mother pairs in each arm (n=400 participants total). 100 children in each arm (n=200)

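### The 82 infants per arm cannot be reproduced at alpha 0.05 (two-sided methods give 56–71), and the sections disagree on the number of older children and on a maximum of 104

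*Combined protocol and SAP*

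**What the plan says.** **Sample-size justification (Subject Children, Section 2, item C).** The control rate comes from a local survey in which "stunting prevalence is 25% in children <5 years". The hypothesis is a 75% reduction at 3 months of age, entered as 6.5%. The conclusion is "At 80% power, this would require a sample size of 82 infants in each arm". The allowance for losses and for a smaller effect comes after that figure: "we aim to recruit 100 infants in each arm if external funding is obtained". For the older cohort: "We also estimate 50 children 6-59 months in each arm, that is 100 children". With up to 20 children in the acceptability phase, this makes the item's total: "Indicate how many children you propose to enroll in the study: 320".

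**Other statements of size.**
- Project Information: "Maximum number of human subjects (or records/specimens to be reviewed) 104".
- Study Population, Phase B: "We anticipate enrolling up to 50 mother-infant dyads in each of two arms and 50 children in each of two arms".
- Study Design: "Sample size: 100 infant-mother pairs in each arm (n=400 participants total). 100 children in each arm (n=200". No funding condition is attached.
- Participant Demographics table: entries of 200 and 300, which sum to 500.

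**Analysis settings.** The Statistical Analysis Plan gives an alpha of 0.05 and names Pearson's chi-square and Fisher's exact test for categorical variables. It does not state sidedness. Its alpha is given for the analysis, not for the sample-size calculation.

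**The concern.** A sample-size statement should be checkable from its own inputs. Here the two proportions, the power and equal arms are given, but they do not lead to 82 at the only alpha in the documents. A reader therefore cannot tell which test, alpha or power the design rests on.

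The second problem is which size is planned. Study Design doubles the older-child cohort relative to the other two sections that state it, and the overall maximum is smaller than every total. The 80% claim is attached to 82 infants per arm, while the Phase B description allows no more than 50 dyads per arm and gives no power or precision for that size. At stake are the number of older children planned, the meaning of the maximum, and the power that applies if only the smaller dyad cohort is recruited.

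**Working it through.** **Inputs.** p1 = 0.25, p2 = 0.065, power 80%, equal arms (item C); alpha 0.05 (Statistical Analysis Plan). Two-sided testing is my assumption; one-sided results are also shown.

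d = 0.185, d² = 0.034225. Mean rate p̄ = (0.25 + 0.065)/2 = 0.1575. 2p̄(1−p̄) = 0.26539. p1(1−p1) + p2(1−p2) = 0.1875 + 0.060775 = 0.248275.

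**Attempt to reproduce 82 (two-sided 0.05, 80% power).**
- Pooled formula: n = [1.960√0.26539 + 0.8416√0.248275]² / 0.034225 = (1.0097 + 0.4194)² / 0.034225 = 59.7, so 60.
- Continuity-corrected: (n/4)[1 + √(1 + 4/(nd))]² with n = 59.67 gives (59.67/4)(1 + 1.1672)² = 70.06, so 71.
- Unpooled: (1.960 + 0.8416)² × 0.248275 / 0.034225 = 56.9, so 57.
- Arcsine: 56.
- Fisher's exact, by enumeration: power 0.793 at 65 and 0.801 at 66, so 66.

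The range is 56–71. One-sided 0.05 gives 44–58, further from 82. The exact 75% reduction (6.25%) gives 54–68 two-sided. A treated rate of 7%, twice the quoted US 3.5%, gives 60–75. None reaches 82.

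**Settings that would reach 82.** At 90% power the simple pooled formula gives 81.5, so 82; other formulas give 75 (arcsine), 77 (unpooled), 80 (pooled) and 90 (continuity-corrected). At 80% power, a two-sided alpha of 0.0148 (pooled) or 0.0262 (continuity-corrected) also gives 82. An allowance of 20% for losses on Fisher's 66 gives 66/0.8 = 82.5, but item C adds its allowance after 82. None of these settings is in the documents.

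**Power at the stated sizes (two-sided 0.05).** Pooled formula: z = (d√n − 1.960√0.26539)/√0.248275. At n = 82, z = (1.6753 − 1.0097)/0.4983 = 1.336, or 90.9%. At n = 50, z = (1.3081 − 1.0097)/0.4983 = 0.599, or 72.5%. The continuity-corrected version replaces d by d − 1/n.

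| Infants per arm | Continuity-corrected | Fisher exact | Pooled formula | Exact chi-square |
|---|---|---|---|---|
| 82 | 86.7% | 89.0% | 90.9% | 92.3% |
| 50 | 62.4% | 64.4% | 72.5% | 76.5% |

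These are before losses. The 25% is a prevalence in children under five, used here at 3 months. Keeping the ratio 0.065/0.25 = 0.26, power at 50 per arm (Fisher to exact chi-square) is 32–49% for a 15% control rate, 49–65% for 20% and 77–85% for 30%.

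**Counts.**

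| Section | Dyads per arm | Older children per arm | Total |
|---|---|---|---|
| Project Information | – | – | maximum 104 |
| Study Population, Phase B | up to 50 | 50 | 2×50×2 + 2×50 = 300 people |
| Subject Children, item C | 82 needed; 100 if funded | 50 | 200 + 100 + 20 = 320 children |
| Item C, Phase B with mothers | 100 if funded | 50 | 200 + 200 + 100 = 500 people |
| Participant Demographics | – | – | 200 + 300 = 500 people |
| Study Design | 100, no condition | 100 | 400 + 200 = 600 people |

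The 82 per arm alone means 164 infants, also above 104.

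**The case against.** **The calculation may be sound with settings that were not written down.** Item C gives no alpha, and the 0.05 is borrowed from an analysis section written in the past tense. This stands in part. The documents support saying that 82 is not reproducible at 0.05. They do not show that anyone made an arithmetic slip, nor that the calculation was really run at 90% power, though a reader might infer either.

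**The discrepancy is harmless.** For the infant comparison at 82 or 100 per arm this stands. A reader might infer from a wrong sample size that the trial is short of infants. At two-sided 0.05 the stated 82 exceeds what the stated effect needs, so that inference fails.

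**Fifty against 100 dyads is not a contradiction.** Item C makes 100 conditional on external funding, so up to 50 can be read as the unfunded size. I accept this; on dyads, the fault in Study Design is only that it drops the condition. Funding does not explain the older children, because item C lists 50 per arm beside the funded 100 infants, while Study Design says 100.

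**The 104 may count something narrower.** It would hold 100 dyads counted as units, for example. That is possible, but the field refers to human subjects and nothing says so.

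**It is a pilot.** A pilot need not have 80% power, and the text supplied names no primary outcome; an outcome-measures attachment is listed but not included. So the figures at 50 per arm describe one binary endpoint and do not show the pilot to be badly designed. They matter because the plan offers a power claim and Aim 2 is framed as a hypothesis test.

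**Conclusion.** The point holds in three limited parts.

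1. At alpha 0.05 and 80% power, 82 per arm is not reproducible. It exceeds the two-sided results by 11 (82 − 71) to 26 (82 − 56) infants per arm. The discrepancy is conservative on that alpha, and its source is unknown.
2. The planned sizes are unreconciled: 50 against 100 older children per arm, a funding condition present in one section and absent in another, and a maximum of 104 against totals of 300, 320, 500 and 600.
3. The 80% statement does not extend to 50 dyads per arm, where power for the hypothesised stunting difference is between 62% and 77% before losses.

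Parts 1 and 3 assume the SAP's alpha applies to the design. The power figures also assume two-sided testing and 25% control stunting at 3 months. Part 2 rests on the text alone and is the firmest. This should be fixed, but it does not show that the infant comparison at 82 or 100 per arm is underpowered.

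**What to change.** - In item C, state alpha, sidedness and test. At two-sided 0.05, either restate N for 80% power (60 by the pooled formula, 66 for Fisher, 71 with continuity correction) or restate power at 82 as about 87–92% according to method. If other settings gave 82, state them.
- Give one planned size per cohort, dyads per arm and older children per arm, with any funding condition attached wherever it appears. Say what the 104 counts. Reconcile Project Information, Study Population, Participant Demographics, item C and Study Design.
- If the unfunded size of up to 50 dyads per arm applies, say that the 80% figure does not cover it, and give the power at 50 by the chosen method with its assumptions.

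These are text changes and need no extra participants. The cost is a less favourable stated power if 50 dyads per arm is the operative size.
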